3.5 Intervention Throughout the 8 weeks (total) of this trial, we will ask all participants to discontinue use of their prevalent SU but maintain other glucose-lowering medications (e.g. insulin) at unchanged doses. We will then prescribe linagliptin for 4 weeks and glipizide for 4 weeks, in a randomly determined order. DPP-4 inhibitors are an attractive class of medications to lower blood glucose among patients at high risk of hypoglycemia because they enhance the actions of endogenous insulin, with little effect on insulin secretion or action when a source of oral glucose is absent. DDP-4 inhibitors may also have beneficial effects on microvascular complications, including CKD, independent of glucose.^{67,68} Linagliptin is particularly attractive for patients with CKD because it is primarily eliminated through non-renal routes and does not require dose adjustment or increased monitoring for adverse effects, even with advanced CKD.^{64,65} We will administer linagliptin at its standard fixed dose of 5 mg daily. For comparison, we will administer glipizide at a fixed dose of 5 mg daily. We selected glipizide because it has a relatively short half-life and is therefore commonly used in patients with CKD. While individuals will differ in their hypoglycemic responses to these medications and doses, we anticipate that mean glycemia will change to a similar extent with each intervention when averaged across participants. In addition, we will adjust for mean CGM blood glucose when comparing differences in hypoglycemia and glucose variability.

3.5.1 Randomization Each participant will be prescribed linagliptin for 4 weeks and glipizide for 4 weeks. The order of these interventions will be randomly assigned by the Northwest Kidney Center Pharmacy, which will dispense all study medications. There will be no stratification or blocking.

3.5.2 Blinding Participants will not be blinded to treatment assignment in order to reduce cost and maximize patient safety. However, data for the primary study outcome (time in range measured by CGM) will be masked to participants, and study staff and investigators will be given only coded treatment assignments (“A” and “B”) until data analyses are completed. In this setting, lack of participant blinding is unlikely to bias results.

4. Study procedures.

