5.1 Data analysis. All analyses will be performed according to intention-to-treat, meaning that all participants who contribute data during treatment with linagliptin and glipizide will be included in analyses regardless of adherence or adverse effects. The primary study outcome will be glucose time in range (TIR, proportion of CGM glucose readings 70-180 mg/dL), a clinically relevant outcome that can be tested with high power because of its broad anticipated range within the study population and precise ascertainment using CGM.^{35,70,71} We will summarize time in range by treatment assignment, along with secondary outcomes including TBR (< 70 mg/dL), hypoglycemia characteristics (episode number, nadir glucose, awareness, clinical severity), time above range (TAR), standard deviation of blood glucose concentration, mean blood glucose concentration, biomarkers of inflammation and oxidative stress, and urine albumin excretion rate. We will test differences in these outcomes by treatment assignment using linear regression (for continuous outcomes, using log transformation as needed) or using Poisson regression (for rate data). Models will be adjusted for mean CGM blood glucose to account for potential differential effects of linagliptin and glipizide on mean blood glucose.

5.2 Power. Using the cross-over study design, two-sided alpha of 0.05, and glucose time in range (TIR quantified as proportion of time) as primary outcome, and assuming a TIR standard deviation of 19.5% (similar to published values^{70,71}) and within-person correlation of TIR 0.7, we calculated a need for 24 participants (each studied on linagliptin and on glipizide) to detect a 10% difference in TIR between treatment assignments with 90% power. Notably, power depends on the difference in TIR between treatment groups, rather than mean TIR (which we expect to be between 25% and 50%), as long as mean TIR is not near zero. Because the effect size (10% difference in TIR) and within-person correlation of TIR are not known in this population, we also present power for different combinations of these variables using a fixed sample size of 24 in **Table 4**. We have excellent power for the most likely range of standard deviation and for clinically relevant treatment effects.

Table 4. Power for intervention study

Difference in time in range (%)	Within-person correlation of time in range		
	0.6	0.7	0.8
8%	62%	74%	89%
10%	80%	**90%**	98%
12%	92%	97%	> 99%

14%	98%	> 99%	> 99%

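### The planned model has no period term and treatment order is not blocked in 24 people, so part of any period effect can enter the treatment estimate; the likely size is modest and the remedy is cheap

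*Combined protocol and SAP*

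**What the plan says.** On allocation, section 3.5.1 says "The order of these interventions will be randomly assigned by the Northwest Kidney Center Pharmacy", and then: "There will be no stratification or blocking". It gives no allocation ratio.

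On analysis, section 5.1 says: "We will test differences in these outcomes by treatment assignment using linear regression" (Poisson regression for rates). The one covariate named is mean CGM glucose. Neither period nor sequence is mentioned, and no within-person term is named, although the power calculation in section 5.2 relies on pairing.

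Section 3.2 discusses carry-over and explains why there is no wash-out. It does not discuss period effects. Section 4.6.5 allows a participant with fewer than 4 days of CGM to be replaced, without saying which sequence the replacement receives.

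**The concern.** In a two-period cross-over, a difference between periods that has nothing to do with the drugs cancels out of the treatment comparison in two ways: the two sequences are the same size, or the model contains period. This plan secures neither. If the sequences come out unequal, one drug is observed more often in the second period, and the treatment estimate picks up part of the period difference.

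A period effect is possible here. Everyone stops a prior sulfonylurea at entry, so monitoring begins about 22 days after stopping in period 1 and about 50 days after in period 2. Participants also take at least four finger-stick readings a day during monitoring, which they can see and may act on later. At stake is a modest distortion of the primary comparison that the planned analysis would neither remove nor reveal.

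**Working it through.** **Inputs.** From section 5.2: 24 participants, "two-sided alpha of 0.05", a 10-point difference in time in range (TIR), SD 19.5 points and "within-person correlation of TIR 0.7". Assumed: 1:1 simple randomisation; all 24 people supply both periods; a period effect of 3 to 6 TIR points, with 2, 5 and 10 points used in the simulations. The documents give no period effect.

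**1. The plan's own figure.** SD of the within-person difference = 19.5 × √(2 × (1 − 0.7)) = 15.10. Required N = (15.10 × (1.960 + 1.282) / 10)² = 23.97, so 24. SE = 15.10 / √24 = 3.08, giving 90.0% power. All cells of Table 4 reproduce within one point. The plan therefore used a paired normal approximation without a period term. A t-based calculation (23 df) gives 87.4% at N = 24.

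**2. Chance of unequal sequences.** With Binomial(24, 0.5), P(12:12) = C(24,12) / 2²⁴ = 16.1%, so P(unequal) = 83.9%. The mean of |n1 − n2| / 24 is 0.161, about one sixth.

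**3. Period not fitted.** Let τ be the treatment effect (linagliptin minus glipizide) and π the period effect (period 2 minus period 1). The expected within-person difference is τ + π in the glipizide-first sequence (n1 people) and τ − π in the linagliptin-first sequence (n2 people). The overall mean is τ + π × (n1 − n2) / 24. Without covariates, this holds whether or not a subject term is in the model.

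**4. Period fitted.** The estimate is the average of the two sequence means. Its variance is the balanced variance times 24² / (4 × n1 × n2), for example 576 / 560 = 1.029 at 10:14 and 576 / 512 = 1.125 at 8:16.

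| Split (either way) | Chance of this or worse | Bias share, period not fitted | Bias for π = 3 / 6 | Variance factor, period fitted | Power, normal | Power, t (22 df) |
|---|---|---|---|---|---|---|
| 12:12 | (exactly: 16.1%) | 0 | 0 / 0 | 1.000 | 90.0% | 87.3% |
| 10:14 | 54.1% | 1/6 | 0.5 / 1.0 | 1.029 | 89.2% | 86.3% |
| 9:15 | 30.7% | 1/4 | 0.75 / 1.5 | 1.067 | 88.1% | 85.1% |
| 8:16 | 15.2% | 1/3 | 1.0 / 2.0 | 1.125 | 86.4% | 83.2% |

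The bias columns and the last three columns belong to different analyses and do not add up. Averaged over all splits, the variance factor is 1.048 and t-based power with period fitted is 85.7%, against 87.3% with a guaranteed 12:12.

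**5. Simulation (100,000 replicates per scenario, paired differences, no mean-glucose covariate).**
- With no period effect and no period term, the SE is 3.08 to 3.09 at 12:12, 10:14 and 8:16, so imbalance alone costs nothing.
- With no period term, type I error for period effects of 2, 5 and 10 points is 5.4%, 6.9% and 10.1% at 8:16, and 5.0%, 4.6% and 3.7% at 10:14. Averaged over the randomisation it is about 5%.
- Even at 12:12, an unmodelled period effect widens the spread of the differences. For 5 points the variance goes from 15.10² ≈ 228 to about 228 + 25 × 24/23 ≈ 254. Power falls to about 85%, and to about 77% for 10 points, against about 87% with the term.

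**The case against.** Unrestricted allocation is valid, openly stated and unpredictable. Blocking alone gains about 1.6 points of power on average (87.3% against 85.7%). The split of 8:16 is unfavourable rather than typical; at a typical 10:14, an assumed 3 to 6 points gives 0.5 to 1 point of bias against an SE of about 3.1. All of that stands.

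The documents also weaken some sources of a period effect. Recruitment is mainly from CANDY, itself a CGM study, so many participants will have worn a sensor before. CGM results are masked. Monitoring falls in the last 6 days of both periods, so only a difference between periods matters. Adjusting for mean CGM glucose might absorb a period effect acting through mean glucose. These points lower the plausible size, but they do not put period in the model.

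A reader might infer two stronger things. One is that unequal sequences both bias the planned analysis and reduce its precision. They do not: the variance factor applies only when period is fitted, and the bias only when it is not. The other is that the design makes the treatment estimate biased as such. The documents do not support that either: the bias depends on the realised split and on a period effect whose size is nowhere given, and it is zero on average over the randomisation. That average does not help a single trial once its split is fixed, which is why the point remains.

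**Conclusion.** The point holds as a modest, cheaply corrected gap. The missing period term is the main weakness and the lack of blocking is secondary. Under the planned model, about one sixth of any period effect enters the estimate at a typical split, and one third at a split that (or worse) has a 15% chance. With an assumed 3 to 6 points, that is 0.5 to 2 TIR points across those two splits, against a target of 10. Omitting the term also costs about 2 points of t-based power at 12:12 if the period effect is 5 points. With period fitted, the remaining cost of simple randomisation is an average variance loss of about 5%.

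This rests on 1:1 simple randomisation, complete data in both periods, an additive period effect, no carry-over (as the plan expects), and figures that leave out the mean-glucose covariate. The trial is sized at exactly 24 with no stated dropout allowance, so it has little precision to spare.

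**What to change.** 1. **Main change, section 5.1.** Specify a within-person model for continuous outcomes (a mixed model with a participant effect, or the equivalent analysis of paired differences) with treatment and period as fixed effects. Make the change before the A/B treatment codes are broken. Cost: one degree of freedom, which takes t-based power at 12:12 from 87.4% to 87.3%.

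2. **Cheap addition, section 3.5.1.** Replace the sentence that rules out blocking with wording such as: *The pharmacy will prepare a concealed list in randomly permuted blocks of varying size, giving 12 participants per sequence; block sizes will be known only to the pharmacy. A replacement participant takes the sequence of the person replaced.* Without the last sentence, a 12:12 list does not secure 12:12 among those analysed. Cost: one list at the pharmacy that already assigns the order, and slight predictability. Varying block sizes limit that predictability, and it matters less when everyone receives both drugs.

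If enrolment is already complete, the period term alone removes the period bias at whatever split occurred.

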3.1 Overview This is a proof-of-concept clinical trial testing the effects of linagliptin *versus* glipizide on glucose variability among patients with type 2 diabetes and stage 3-4 CKD. Linagliptin is a dipeptidyl peptidase-4 (DPP-4) inhibitor proven to reduce blood glucose among patients with type 2 diabetes and normal GFR, with an incidence of clinical hypoglycemia that is lower than that of sulfonylureas (SU).⁶³ Linagliptin is primarily eliminated through non-renal routes and does not require dose adjustment with impaired GFR. In CKD, fixed-dose Linagliptin reduces hemoglobin A1c (compared with placebo) without a significant increase in clinically-recognized hypoglycemia.^{64,65} We hypothesize, among patients with type 2 diabetes and CKD, that Linagliptin, compared to Glipizide (a SU), will increase glucose time in range (TIR) (ascertained using CGM) while reducing glycemic variability and time below range (TBR) and exerting similar effects on mean glycemia. Results may have direct implications for patient care, suggesting that use of linagliptin as a SU-sparing agent may improve patient safety, and will provide a useful framework for future studies targeting glycemic control while minimizing hypoglycemia in the CKD population.

3.2 Study Design This is a cross-over trial in which each participant is treated with both linagliptin and glipizide, one medication at a time. Cross-over trials increase power and reduce cost by studying each participant on each treatment and comparing changes within each individual, as opposed to across individuals. We have successfully completed a crossover trial of similar size and duration with excellent recruitment and retention.⁶⁶ The main limitation of cross-

over trials is the potential for treatment carry-over, in which effects of treatment from the first treatment period extend into the subsequent treatment period(s). Because the effects of linagliptin and glipizide on glucose are rapid, we have little concern for carry-over effects on glucose as measured by CGM, our primary outcome. (Hemoglobin A1c and other longer-term glycemic markers will only be evaluated in secondary, exploratory analyses.) Given rapid effects, we will have short treatment periods (4 weeks), which will enhance retention and adherence. A wash-out phase is not appropriate for this study because carry-over effects are not expected and withdrawal of both glucose-lowering medications would lead to relative hyperglycemia

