Each participant will undergo blinded CGM for the last 6 days of each 4-week treatment period (**Figure 3**). During each CGM period, participants will also be asked to self-monitor blood glucose concentrations, and blood and urine samples will be collected for measurements of inflammation, oxidative stress, and albuminuria.

4.1. Continuous glucose monitoring.

We will use Medtronic Enlite glucose sensors coupled to iPro2 recorders (**Figure 4**). The Enlite is an advanced glucose sensor, offering accurate glucose monitoring over days of use.

An Enlite will be provided to participants at study visits 2 and 4. Study staff will insert the sensor into the subcutaneous tissue of the abdomen with the use of a disposable introducer needle. The sensor is attached to the iPro2 recorder, which with its predecessor (iPro recorder) has proved reliable in numerous clinical studies as a masked glucose

Figure 4. Medtronic continuous glucose monitor

sensor. Participants will be instructed in the use of the device including collection of self-monitored blood glucose concentrations for device calibration using a study-provided glucose meter. A guide booklet will be provided for the participant to take home. The participant will be instructed to contact the site staff if any appreciable skin reaction occurs or for any other concerns or questions. Participants will return all CGM equipment after 6 days, and study personnel will upload the data. Participants who do not obtain an adequate amount of CGM glucose values will be asked to repeat use of the CGM so that a sufficient amount of data is obtained. CGM data will be masked to participants, study staff, and investigators.

4.2. Self-monitored blood glucose. Participants will be asked to monitor blood glucose concentrations for calibration purposes. Participants will be provided with a Blood Glucose Meter and test strips. They will be asked to perform at least 4 finger-stick blood glucose measurements per day. Data from the Blood Glucose Meter will be directly uploaded at the end of the trial.

4.3. Blood and urine collections. At least 3 nonfasting blood samples will be collected at study visits 3 and 5. Whole blood, serum and plasma samples will be aliquoted, and stored at -80°C as per Kidney Research Institute protocols. Spot urine collections will also be collected from patients at study visits 3 and 5.

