4.6.4. Study Visit 4 At the fourth study visit, the CGM device will be reintroduced by the study staff. They will place the CGM device, and thoroughly describe plans for trouble-shooting the CGM device. The study staff will also provide a study glucose meter and test strips for self-

monitored blood glucose (SMBG) testing, explain expectations for tracking SMBG at home, provide logs for SMBG, and demonstrate proper use of the logs. Adverse effects will be assessed.

4.6.5. Study Visit 5 At the fifth study visit, the CGM device will be removed from the subject by the study staff, and the SMBG log will be turned in to the study staff. The subject will cease taking the second study medication on this day, and return any remaining prescription to the study staff. The visit will include a blood draw, and spot urine collection. Adverse effects will be assessed.

24-hour contact information will be given to all participants for questions that arise during the CGM periods. Participants who do not complete at least 4 days of CGM will be asked to repeat measurements or will be replaced by an alternate participant

Table 3. Schedule of Procedures

Procedure	Screening	Visit 1	Visit 2	Visit 3	Visit 4	Visit 5
Informed Consent	X					
Medication inventory	X					
Medical History	X	X				
Blood draw	*X			X		X
Medical History Questionnaire		X				
Physical measurements (height, weight, vital signs)		X				
Randomization		X				
Medication Prescribed		X		X		
Urine-spot				X		X
CGM Provided			X		X	
CGM Returned				X		X
Log provided			X		X	

Log returned				X		X
AE		X	X	X	X	X

* Blood draw at the screening visit will be completed only if creatinine and hemoglobin A1c values are not otherwise available within 90 days prior to the screening visit.

5. Statistical analysis

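### Section 5.1 names no participant or period term for a cross-over that sections 3.2 and 5.2 justify and size as a within-person comparison

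*Combined protocol and SAP*

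**What the plan says.** Section 5.1 is the only analysis section. For TIR and the secondary outcomes it states: "We will test differences in these outcomes by treatment assignment using linear regression" for continuous outcomes, and Poisson regression for rates. It then adds: "Models will be adjusted for mean CGM blood glucose". No other covariate is named. Nowhere does the document mention a participant effect, a paired difference, a mixed model, a robust variance, or a period or sequence term.

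Two other sections presume a paired analysis. Section 3.2 gives as the reason for the cross-over that it works by "comparing changes within each individual, as opposed to across individuals". Section 5.2 opens with "Using the cross-over study design, two-sided alpha of 0.05, and glucose time in range" and, with a TIR standard deviation of 19.5 points, reports: "within-person correlation of TIR 0.7, we calculated a need for 24 participants", for 90% power at a 10-point difference.

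Three further statements bear on the model. On treatment order, section 3.5.1 says: "There will be no stratification or blocking". On planned wear, section 4 says: "Each participant will undergo blinded CGM for the last 6 days of each 4-week treatment period". On the minimum, the end of section 4.6.5 says: "Participants who do not complete at least 4 days of CGM will be asked to repeat measurements" (or will be replaced).

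**The concern.** The sample size depends on an analysis that the analysis section does not specify. Linear regression by treatment could mean ordinary least squares on 48 participant-period records, a regression of within-person differences, or a mixed model, each with or without period. With 24 participants these can differ in estimate, standard error and degrees of freedom. The glucose covariate widens the gap: a pooled model mixes the between-person and within-person glucose slopes, while a difference model uses only the within-person slope.

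What is at stake for TIR is the efficiency for which the cross-over was chosen. If the choice stays open until data are in hand, there is also discretion over the primary test. The period term is a separate gap, because reading pairing into 5.1 does not supply one.

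**Working it through.** **Inputs from section 5.2:** SD 19.5 points, within-person correlation ρ = 0.7 (0.6 to 0.8 in Table 4), n = 24, difference 10 points, two-sided α = 0.05.

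**1. The plan's own figure.** SD of the within-person difference = 19.5 × √(2 × (1 − 0.7)) = 15.10. Paired SE = 15.10/√24 = 3.08. Required n = ((1.96 + 1.2816) × 15.10/10)² = 23.97, so 24. Power = Φ(10/3.08 − 1.96) = 90.0%. The same formula reproduces every cell of Table 4 within 1 point (for example 61.3% against the printed 62% at 8 points, ρ = 0.6). Section 5.2 is therefore a paired, unadjusted normal approximation.

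**2. Section 5.1 taken literally, no covariate.** Independent-record SE = 19.5 × √(2/24) = 5.63. Ratio to the paired SE = 1/√(1 − ρ) = 1.83 at ρ = 0.7 (1.58 at 0.6, 2.24 at 0.8). The treatment estimate itself is the same and still varies with SD 3.08. The literal test rejects when the estimate exceeds 2.013 × 5.63 = 11.3 points (t, 46 df). Its power at 10 points is then about 33%, and its type I error about 0.02%.

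**3. With the glucose covariate.** The documents give no correlation between TIR and mean glucose, so all of the following is assumed: no treatment effect on mean glucose, within-person glucose correlation 0.7, ρ = 0.7. The literal model is least squares on 48 rows with treatment and glucose. The comparator is the TIR difference regressed on the glucose difference (22 df, no period term). There were 40,000 simulated trials per case, with power at 10 points.

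| TIR–glucose correlation, between / within person | Literal mean SE | True SD of its estimate | Ratio | Power, literal | Power, paired |
|---|---|---|---|---|---|
| 0 / 0 | 5.57 | 3.16 | 1.76 | 36% | 85% |
| −0.5 / −0.5 | 4.83 | 2.71 | 1.78 | 54% | 94% |
| −0.8 / −0.8 | 3.34 | 1.88 | 1.78 | 94% | 99.9% |
| −0.7 / −0.5 | 4.29 | 2.73 | 1.57 | 68% | 94% |
| −0.9 / −0.3 | 3.89 | 3.22 | 1.21 | 74% | 89% |
| −0.5 / −0.7 | 4.61 | 2.30 | 2.00 | 61% | 99% |

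Type I error of the literal model was 0.03% to 1.9% across these cases. A wider analytic grid of 540 assumed combinations (ρ 0.6 to 0.8, glucose correlation 0.5 to 0.9, TIR–glucose correlations 0 to −0.95) gave ratios from 1.07 to 5.6, median 1.74, and none below 1. The direction is stable. The size is not.

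**4. Period.** Let n1 and n2 be the numbers in the two sequences. Without a period term the mean paired difference equals the treatment effect plus or minus (n1 − n2)/24 of the period effect: 4/24 = 0.17 at 14:10 and 6/24 = 0.25 at 15:9. Reading unblocked order as simple 1:1 randomisation, Binomial(24, 0.5) gives 16% for 12:12, 69% for 14:10 or closer, and 31% for 15:9 or worse. The documents give no period effect, so the shift in points cannot be stated. The term costs a factor √(24²/(4 × n1 × n2)) in SE: 1.014 at 14:10 and 1.033 at 15:9. Power by t-test is 87.3% at 12:12, 86.3% at 14:10 and 85.1% at 15:9.

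**5. Power by t-test.** A paired t-test (23 df, noncentral t) with 24 participants has 87.4% power at 10 points. It reaches 90% at 10.44 points. Table 4 on this basis:

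| Difference | ρ = 0.6 | ρ = 0.7 | ρ = 0.8 |
|---|---|---|---|
| 8 | 58% | 70% | 86% |
| 10 | 77% | 87% | 97% |
| 12 | 90% | 96% | >99% |
| 14 | 96% | 99% | >99% |

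**6. Episode counts.** Planned wear is 6 days and the minimum is 4, so exposure can differ by up to 6/4 = 1.5-fold between complete periods. No count model was computed.

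**The case against.** The strongest reply is that sections 3.2 and 5.2 already settle the matter. The comparison is within individuals, and linear regression does not exclude a regression on within-person differences. That stands as evidence of intent. A reader might infer from 5.1 that the plan means to ignore the pairing, or that the TIR result could be falsely positive. The documents support neither: the rest of the plan points to pairing, and the literal model errs on the conservative side. Intent still does not tell the analyst which paired model to use, how glucose enters it, or whether period is included.

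A reader might also want a single multiplier for the glucose-adjusted standard error. The documents do not support one. Equal between- and within-person correlations give about 1.8 whatever their size, a stronger between-person correlation gives less, and a stronger within-person correlation gives 2.0 or more.

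On period, randomised order keeps the estimate unbiased over repeated randomisations, and the likely splits are mild. Both statements are true. The term guards against a chance imbalance in the one trial that is run, and no actual harm has been shown.

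On counts, 5.1 reserves Poisson regression for rates, which already implies an exposure denominator, and 1.5-fold is the extreme contrast. Only an unquantified request for detail on secondary outcomes remains.

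On power, the normal approximation is a common planning formula. The gap of 2.6 points is small beside the 80% to 98% that Table 4 shows across correlations at 10 points. It does not show that the trial is underpowered. Nor is 87% the power of the glucose-adjusted analysis, which ranged from 85% to 99.9% in the assumed cases.

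**Conclusion.** The point holds as an under-specified primary model that should be fixed; it does not invalidate the trial. Section 5.1 lacks the participant and period terms that the cross-over needs, and it does not match the paired calculation in 5.2. Followed to the letter without a covariate, it would report a TIR standard error of 5.63 instead of 3.08 points (1.83 times, on the plan's own SD and ρ = 0.7) and would lose most of the planned power. With the glucose covariate the standard error is still too large in every case examined, but by an amount that rests on assumed correlations.

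The consequence for TIR is lost power. It would arise only if an analyst followed 5.1 against 3.2. The period term and the restated power are worth having even if pairing is taken for granted, although the bias that the period term prevents cannot be sized from the documents. The point about counts is secondary and unquantified.

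**What to change.** **Section 5.1, continuous outcomes.** Specify a within-participant model with fixed treatment and period effects, in one of two forms:
- within-person differences regressed on sequence coded ±1, so that the intercept is the period-adjusted treatment effect; or
- a linear mixed model with treatment, period, a random participant intercept and small-sample degrees of freedom.

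If mean glucose stays as a covariate, enter its within-person difference in the first form, or split it into within- and between-person parts in the second. With complete pairs the two forms then agree. A mixed model with raw mean glucose blends the two slopes and is not interchangeable with the difference model.

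**Section 5.1, episode counts.** Account for the participant (for example by a robust or overdispersed variance), include period, and use CGM wear time as offset.

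**Section 5.2.** Label the 90% and Table 4 as normal approximations for an unadjusted paired comparison. Restate the base case as about 87% (paired t-test, 24 participants; 90% power at about 10.4 points) and recompute Table 4 on that basis.

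**Cost.** A few sentences, a slightly lower stated power, one degree of freedom, and about 1% to 3% in standard error at splits of 14:10 to 15:9. No new data or participants are needed.

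### Section 5.2: the 90% power for 24 participants is consistent with a normal approximation that is mildly optimistic at 24 pairs; a paired t on the same inputs gives about 87%, and 90% at about 10.4 points

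*Combined protocol and SAP*

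**What the plan says.** Section 3.2 sets the design: "This is a cross-over trial in which each participant is treated with both linagliptin and glipizide". Section 5.2 gives the power inputs. The test level comes from "Using the cross-over study design, two-sided alpha of 0.05", and the SD from "assuming a TIR standard deviation of 19.5" per cent. The within-person correlation is 0.7. The result is that the trial needs "24 participants (each studied on linagliptin and on glipizide) to detect a 10% difference in TIR between treatment assignments with 90% power".

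Section 5.2 acknowledges that the effect size and the correlation are not known in this population, and adds Table 4: "we also present power for different combinations of these variables using a fixed sample size of 24". The table covers differences of 8, 10, 12 and 14 points and correlations of 0.6, 0.7 and 0.8. The section ends: "We have excellent power for the most likely range of standard deviation and for clinically relevant treatment effects".

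On the analysis, section 5.1 says "We will test differences in these outcomes by treatment assignment using linear regression" for continuous outcomes, and "Models will be adjusted for mean CGM blood glucose". Neither section says whether the power figures use a normal or a t distribution.

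**The concern.** With 24 pairs, the SD of the within-person difference has to be estimated from 23 degrees of freedom. A power formula that treats that SD as known and uses the critical value 1.960 overstates the power of a small-sample test run at a true two-sided 0.05. If the 90% comes from such a formula, the plan states slightly more power than the design has on its own inputs. A reader who later weighs a null or borderline result against the 10-point difference would be using a detectable difference that is slightly too small. Because the method is not named, the reader cannot tell which calculation the figure refers to.

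**Working it through.** **Inputs, all from section 5.2.** TIR SD 19.5 points; within-person correlation r = 0.7 (Table 4 also uses 0.6 and 0.8); two-sided alpha 0.05; 24 pairs; difference 10 points (Table 4: 8, 10, 12, 14). The calculation assumes 24 complete pairs and no covariate adjustment.

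**Step 1. SD of the within-person difference.** SDd = 19.5 × √(2(1 − r)). This gives 17.44, 15.10 and 12.33 for r = 0.6, 0.7 and 0.8.

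**Step 2. Reproduce the plan's figure by the normal approximation.**
- N = (15.10 × (1.960 + 1.282) / 10)² = 23.97, rounded up to 24.
- Standardised effect: 10 / 15.10 × √24 = 3.243.
- Power = Φ(3.243 − 1.960) = 90.03%.

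The stated 24 and 90% are reproduced.

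**Step 3. The same inputs by paired t.** The noncentral t has 23 df, noncentrality 3.243 and critical value 2.069. Power is 87.4%, which is 2.6 points below the headline. The difference with 90% power is 10.44 points.

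**Step 4. Table 4, power in %, at N = 24 and SD 19.5.**

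| Difference | r | Printed | Normal | Paired t | Normal minus t |
|---|---|---|---|---|---|
| 8 | 0.6 | 62 | 61.3 | 57.6 | 3.7 |
| 8 | 0.7 | 74 | 73.7 | 70.0 | 3.7 |
| 8 | 0.8 | 89 | 88.8 | 86.1 | 2.8 |
| 10 | 0.6 | 80 | 80.2 | 76.7 | 3.5 |
| 10 | 0.7 | 90 | 90.0 | 87.4 | 2.6 |
| 10 | 0.8 | 98 | 97.8 | 96.7 | 1.1 |
| 12 | 0.6 | 92 | 92.1 | 89.7 | 2.3 |
| 12 | 0.7 | 97 | 97.3 | 96.1 | 1.2 |
| 12 | 0.8 | >99 | 99.8 | 99.5 | 0.2 |
| 14 | 0.6 | 98 | 97.6 | 96.4 | 1.1 |
| 14 | 0.7 | >99 | 99.5 | 99.1 | 0.4 |
| 14 | 0.8 | >99 | >99.9 | >99.9 | 0.0 |

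The normal column matches the printed value in 11 of 12 cells after rounding. The exception is 8%/0.6, at 61.3 against a printed 62. All 12 match if the SD is 19.43 to 19.45, so rounding of the input probably explains about 0.7 points there. The paired t column matches in only 3 cells, all printed as >99. It would match all 12 only at an SD of about 18.6, not the stated 19.5.

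**Step 5. What would restore 90% by paired t at 10 points.** Any one of these would do: a correlation of at least 0.725 at SD 19.5, an SD of at most 18.7 at correlation 0.7, or 26 pairs (90.04%).

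**The case against.** The strongest reply is that the plan contains no error. The 90% follows from the stated inputs by an accepted planning formula. The gap of 2.6 points is small beside the uncertainty the plan itself discloses: Table 4 runs from 80% to 98% for 10 points across correlations of 0.6 to 0.8, and a correlation of 0.725 instead of 0.70 would restore 90%. For a proof-of-concept trial, a reader of Table 4 would reach the same decision. This stands as to size. It does not make the headline right for a small-sample test on the headline's own inputs.

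A second reply is that section 5.1 prescribes no t test, so the normal figure could be the intended one. The method is indeed only inferred from the match. But testing 24 pairs against 1.96 with an estimated SD gives 89.5% power at a true two-sided alpha of 6.2%, so 90% at 0.05 would still not be met. That test is hypothetical. The 6.2% answers this reply and is not a defect in the plan.

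A third reply is that 87% is not the power of the planned analysis either, because section 5.1 adjusts for mean CGM glucose. This stands in full. The documents give no inputs for the adjusted model. As an illustration under assumed values (22 df), 90% is regained if adjustment removes about 8.6% of the difference variance and none of the effect. Power falls to about 80% if it absorbs 10% of the effect and removes no variance. The replacement figure must therefore be labelled as unadjusted.

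**Conclusion.** The point holds as a small editorial one. On the plan's own inputs, with 24 complete pairs and before adjustment for mean CGM glucose, power for 10 points is about 87% by paired t, not 90%, and 90% is reached at about 10.4 points. Six Table 4 cells are about 2 to 4 points high: the whole 8% row, 10% at correlations 0.6 and 0.7, and 12% at 0.6. The remaining cells differ by 1.2 points or less between the two methods. The arithmetic is firm. That the plan used a normal approximation is a strong inference, not something it states.

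A reader might infer three stronger things that the documents do not support:
- **That section 5.2 contains a miscalculation.** It does not; its figures reproduce under a recognised formula.
- **That the trial is underpowered and must enrol more.** The shortfall is 2.6 points, and section 5.2 already shows power varying far more than that with the correlation.
- **That 87% is the true power of the primary analysis.** The adjusted model's power cannot be computed from the documents, and it could lie on either side of 87%.

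**What to change.** Keep N = 24 and name the method in section 5.2. Restate the headline along these lines:

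*With 24 complete pairs, TIR SD 19.5%, within-person correlation 0.7 and a two-sided 0.05 paired t test, power is about 87% for a 10-point difference and 90% for 10.4 points, before adjustment for mean CGM glucose.*

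Give the t-based values in Table 4 or in a note to it (correlation 0.6/0.7/0.8):
- 8%: 58/70/86
- 10%: 77/87/97
- 12%: 90/96/>99
- 14%: 96/>99/>99

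This is a text edit and a table note. The stated power becomes slightly less favourable; sample size and conduct do not change.
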